Our primary aim is to analyze the impact of CETA in the full study population; however, we have calculated our sample size to ensure our ability to detect differences separately among women who include a partner in the CETA intervention and those who do not. We will include a sample of 400 women, which will give us 80% power to detect an absolute 21% difference between arms. Our primary analysis will be a comparison of intervention and control by risk differences with 95% confidence intervals. We will analyze direct effects of CETA on continuous outcomes (e.g., mental health) with linear mixed models. We will evaluate the impact of potential moderators on retention and mental health outcomes using interaction terms. Micro costing methods will be used to cost all resources utilized and the cost effectiveness of CETA achieving the primary outcome will be evaluated.

We will also qualitatively explore participant and health provider perceptions and experiences of CETA. For this qualitative component we will use a sample of up to 50 participants which will consist of 3 focus group discussion and 10 in-depth interviews from CETA participants who completed CETA sessions in 2023, as well as up to 10 in-depth interviews with CETA providers and healthcare providers from implementing sites. The findings from these qualitative interviews and discussions will be thematically analyzed.

INVESTIGATORS

This evaluation will be conducted by investigators from Boston University (School of Public Health), Wits University (Health Economics and Epidemiology Research Office, Wits Health Consortium), Johns Hopkins University (School of Public Health) and Columbia University (School of Public Health) in close collaboration with the Department of Health of South Africa. Individual investigators are:

Boston University (BU)

Boston University Principal investigator

[name]
Professor
Departments of Epidemiology and Global Health
Boston University School of Public Health (BUSPH)
United States

Co-investigator

[name]
Professor
Department of Global Health
Boston University School of Public Health (BUSPH)
United States

Co-investigator

[name]
Assistant Professor
Department of Global Health
Boston University School of Public Health (BUSPH)
United States

HE²RO (Wits Health Consortium, Wits University)

HE²RO Principal Investigator

[name]
Principal Researcher
Health Economics and Epidemiology Research Office (HE²RO)
South Africa

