The full consent process, including signed informed consent, will be administered by a trained study staff member. The study staff will emphasize the voluntary nature of the study. The full consent form, for those who are eligible and interested in being in the study, will describe the nature and goals of the study and assure subjects their information will be kept confidential. We will explain to subjects the possible treatment options in the study and that they will not get to decide which group they will be in, but rather that we will decide by chance and they will have a 50-50 chance of being in either group. We will explain that if they are randomized to the intervention arm (CETA) their care will be different from the active control (text+safety) arm and the options they have to not participate. It will also be explained that they will be free to withdraw from the study at any time with no risk to the healthcare they receive at the clinic. The consent process will take place in a private space and women will be given adequate time to decide whether they want to participate and will be allowed to leave the clinic and return at a later time to complete the consent process if they choose to. Consent documentation will be done either using a paper form or via electronic consent by having the participant sign the document in REDCap. If an electronic signature is used, it will be on a PDF version of the IRB approved and stamped consent form. This will be done via a tablet in person (as would be done for a paper consent) and the participants will have access to the consent form as the consent process is taking place. Even if participants sign the consent electronically, they can also have a paper copy of the information sheet. As such, no electronic version of the e-consent will be made available to the participants.

For safety reasons, we will inform women that they do not need to take a copy of the consent form if they do not wish to do so in order to minimize disclosure of information since the woman's consent form includes experience with violence.

The consent form will include permission to access their clinic records. The consent form will also state that the subject agrees to complete a baseline questionnaire for our study and that the questionnaire responses can also be linked to the subject's treatment records. Participants will be assured that data

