- Cost and cost-effectiveness: We will estimate the incremental cost-effectiveness of CETA versus active control in achieving the primary study outcome, retained in care and virally suppressed by 12 months, from the provider perspective. If found to be effective, a budget impact analysis will be conducted to estimate the affordability of routine implementation of the intervention at scale.
- Perceptions and acceptability of CETA: Using qualitative focus group discussions and in-depth interviews with both study participants in the treatment arm, CETA providers and healthcare providers. we will also explore the perceptions, acceptability and durability of the intervention, both as a recipient of care and provider and also the feasibility of delivering this intervention which will help inform recommendations for further implementation and scale up of the intervention, which will help inform recommendations for further implementation and scale up of the intervention.

c. Sample Size

Based on the ENHANCE study(85), we estimate that only 40% of those who are unsuppressed will be retained in care and virally suppressed 12 months post-baseline in the control arm. We believe a 20% increase in the percent suppressed and retained between the CETA and control arms would be clinically meaningful. Our primary aim is to analyze the impact of CETA in the full population; however, we have calculated our sample size to ensure our ability to detect differences separately among women who include a partner. With 80% power and 2-sided $\alpha=0.05$, using a chi-squared test for independent proportions our sample size required is 91 per arm (182 total). To have power to detect mediators and moderators (Aim 2), we will increase the sample size to **400 total** with a minimum of 75 women in the CETA arm who include partners (max of 100), which will give us 80% power to detect an absolute 21% difference between arms in women with partners. To get 75 women who include partners in the CETA arm we will have to randomize about 150 women willing to include a partner if randomized to CETA. We will also include at least 75 partners of women, up to 100.

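### The 91 per arm and the 21-point subgroup figure do not follow from the stated 40% control rate, the Summary applies the subgroup figure to all 400 women, and interaction power is not quantified

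*Combined protocol and SAP*

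**What the plan says.** Under Data Analysis, c. Sample Size, the protocol expects that "only 40% of those who are unsuppressed will be retained in care and virally suppressed 12 months post-baseline in the control arm", and adds: "We believe a 20% increase in the percent suppressed and retained between the CETA and control arms would be clinically meaningful". Power is set at 80% with a two-sided 5% level, and the conclusion is that "using a chi-squared test for independent proportions our sample size required is 91 per arm (182 total".

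The section then enlarges the trial: "To have power to detect mediators and moderators (Aim 2), we will increase the sample size to" 400. At least 75 women in the CETA arm (at most 100) are to include a partner, "which will give us 80% power to detect an absolute 21% difference between arms in women with partners". To obtain those 75, about 150 women willing to include a partner are to be randomised. The full-consent section says that "they will have a 50-50 chance of being in either group", so this is about 75 per arm.

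The Summary reports the power differently: "We will include a sample of 400 women, which will give us 80% power to detect an absolute 21% difference between arms". The sentence before it mentions detecting differences separately in women with and without partners, but the power sentence names no subgroup.

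Aim 2 under Objectives names partner involvement as the primary moderator and expects it to enlarge the effect. Data Analysis, e. Moderator Analysis, tests this with an arm-by-moderator interaction term and reports risk differences within moderator levels.

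**The concern.** A sample-size statement should be reproducible from its own inputs. Here two figures are not, and a third is attached to the wrong group of women. A reader of the Summary would believe that the main comparison can detect only 21 points, when it can detect about 14. A reader of the Sample Size section would believe that 75 women with partners per arm are enough for 21 points, when they fall short.

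The fourth issue is different in kind. Going from 182 to 400 women is justified by power for Aim 2, but the only power figure given is for the effect of CETA inside one subgroup. The planned moderator test asks whether two effects differ, which needs far more information. Without a stated detectable interaction, nobody can judge what a non-significant result on the primary moderator would mean.

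**Working it through.** **Inputs.** From the Sample Size section: control rate 40%; increase 20%, read as absolute (60% under CETA) because the next effect is explicitly absolute; 80% power; two-sided 5%; chi-squared test; 75 to 100 CETA women with partners; 400 in total. Allocation 1:1 from the consent text. z values: 1.960 and 0.842.

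**1. The 91 per arm.** Standard chi-squared formula:

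n = [1.960 × √(2·p̄·(1−p̄)) + 0.842 × √(p1(1−p1) + p2(1−p2))]² / d²

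With p1 = 0.40, p2 = 0.60, p̄ = 0.50, d = 0.20:

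- 1.960 × √0.50 = 1.386; 0.842 × √0.48 = 0.583; sum 1.969; squared 3.877; divided by 0.04 = 96.9, so **97 per arm (194)**.
- With continuity correction, (96.9/4) × [1 + √(1 + 4/(96.9 × 0.20))]² = 106.7, so **107 per arm (214)**.

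Other variants for 40% vs 60% also miss 91: unpooled variance 95, arcsine 97, one-sided 77 (86 corrected). Reading the increase as relative (40% vs 48%) gives 604.

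Power at 91 per arm: (0.20 × √91 − 1.386)/√0.48 = 0.753, so **77.4%** (76.3% by exact enumeration, 78.6% unpooled).

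**2. The 21 points in women with partners.** At 75 per arm, 40% vs 61%: p̄ = 0.505, the null term is again 1.386, and the alternative term is √(0.240 + 0.2379) = 0.6913.

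- Power: (0.21 × √75 − 1.386)/0.6913 = 0.626, so **73.4%** (74.8% exact, 74.9% unpooled).
- Difference detectable with 80% power, solving the formula for p2 at n = 75: **22.7 points**.
- Needed for 21 points: (1.386 + 0.842 × 0.6913)² / 0.0441 = 87.8, so **88 per arm**.
- At 100 per arm, the stated maximum matched by a similar number of controls: power **84.9%**, detectable difference **19.7 points**.

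**3. All 400 women.** At 200 per arm and a 40% control rate, 80% power is reached at **13.9 points**. Power for 20 points: (0.20 × √200 − 1.386)/√0.48 = 2.08, so 98.1%. For 21 points it is 98.9%. The 21 in the Summary is the partner-subgroup figure.

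**4. The interaction.** The documents give no effect size or stratum rates, so this step rests on assumptions: a 40% control rate in both strata, and p(1−p) = 0.24 in every cell (rates of 40% or 60%). The splits per arm are 75 with and 125 without a partner, or 100 and 100.

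- 75/125: SE = √(0.48/75 + 0.48/125) = 0.1012. Detectable difference between risk differences: (1.960 + 0.842) × 0.1012 = **28.4 points**. Power for a 20-point difference: 51%.
- 100/100: SE = √(0.48/100 + 0.48/100) = 0.0980. Detectable: **27.4 points**. Power for 20 points: 53%.

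Other CETA rates, with the control rate kept at 40%, moved the detectable difference only between 26.4 and 28.4 points. Under the same variance assumption, a 20-point interaction at 80% power would need about 750 to 800 women in total.

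**The case against.** **The 91 has no consequence for the main comparison.** This stands. The trial was set at 400, about double the corrected 194 or 214. A reader might infer from the arithmetic error that the primary analysis is underpowered; at about 98% power for 20 points, it is not. The Summary errs on the cautious side, and its preceding sentence partly explains where its figure came from.

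**The 21 points lie within the planned range.** This stands in part. With 75 to 100 per arm the detectable difference runs from 22.7 to 19.7 points, and 21 is reached at about 88. If more control women than CETA women fell in the stratum, the shortfall would shrink: 75 vs 100 gives 79% power for 21 points. But the protocol ties its figure to the minimum of 75 and to about 150 willing women, where the shortfall is 1.7 points. It also says that the final number of men could not be confirmed.

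**No interaction power is claimed.** This stands. A reader might infer that the protocol promises 80% power for a moderator effect and fails to deliver it. The text gives a purpose for the larger sample and no number for the interaction. The gap is an unquantified statement, and the 27 to 28 points above are this review's assumption-based figure.

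**Misreading of a null interaction is not planned.** This also stands. Nothing in the protocol says that a non-significant interaction will be taken as equal effects, and risk differences within levels are already foreseen. The moderator section does not repeat the confidence intervals promised for the primary analysis.

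**Conclusion.** Three statements are wrong as written. The required size is 97 per arm (107 corrected), where the protocol has 91. Power for 21 points at 75 women with partners per arm is about 73%, where it has 80%. All 400 women can detect about 14 points, where the Summary has 21. These results need only the stated 40% control rate, an absolute reading of the 20% increase, 1:1 allocation and the standard chi-squared formula.

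In addition, interaction power is not quantified, although Aim 2 is the reason given for 400 women. A detectable difference of about 27 to 28 points is a fair guide, conditional on the assumed stratum rates and split.

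It is tempting to say that a 20% control rate was entered by mistake. Indeed 20% vs 40% with continuity correction returns 91, and 20% vs 41% at 75 per arm gives 80.4% power without correction. This is only a numerical match: the two figures need different formulas, 60% vs 80% also returns 91, and the documents show no such input.

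The error affects reporting and interpretation. It does not affect the validity of the primary analysis.

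**What to change.** - Replace 91 (182) by 97 per arm (194), or 107 (214) if the continuity correction is intended, and state both rates and the formula.
- Restate the partner-subgroup figure as a detectable difference of about 23 points at 75 per arm and about 20 points at 100 per arm, both at a 40% control rate.
- In the Summary, label the subgroup figure as referring to women with partners, in its restated form, and give about 14 points for all 400 women.
- Replace the statement on moderator power by the detectable interaction (about 27 to 28 points, with the assumed rates and splits shown), or call the moderator analyses exploratory. In either case report them with confidence intervals, and say that a non-significant interaction is not evidence of equal effects.

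The cost is text only. The Data Safety and Monitoring Plan records that all one-year follow-ups were complete by March 2025, so recruitment cannot change; the corrections belong in the analysis plan and the trial report. The subgroup figure becomes slightly less favourable at the minimum, and the overall figure more favourable.

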The violence literature encourages intervention with both males and females to effectively address IPV. After a detailed explanation of the intervention, women who consent will be asked if they are willing to include a current male partner in the intervention if they are randomized to the CETA arm. They will be informed that this is not a requirement to be in the study and that they can participate whether or not they want to include their current male partner. We will explain that if the woman is randomized to CETA and a male partner is included, both partners will be invited to participate in CETA *separately*; they would not be counselled together. In our team's experience in Zambia, there were many males interested in participation and who enrolled and remained in CETA treatment throughout. Our qualitative findings indicated that women wanted their partners to join them in treatment and were generally invested in trying to improve the relationship (rather than exit it). We will explain to the woman participant that we will not disclose to the male partner that the woman has reported IPV.

Women who wish to include a partner will be given an information sheet to give to their partner describing the study and inviting them to participate. The information sheet will invite the male to participate in a program that can help improve health and interpersonal relationships and will note that there will be tea/biscuits at the visit. This information sheet that will be given to the male partner will not mention IPV. Those men who are willing to know more about the study and potentially participate will be asked to either attend information sessions at the clinic on a specified time and date or to ring a free study number where they will be given more information about the study. Alternatively, they could complete their contact details and sign the form indicating that they give consent for the study team to contact them. They can then either return the form themselves to a secure designated collection point at the clinic or return it with their partner. Appointments will be made with all those men who indicate they are interested in the program to come to the clinic or meet at alternative secure locations to complete the consent process. The consent will focus on our primary outcome of adherence, and CETA work with the males will focus on increasing healthy behaviors and skill building to support their

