At the clinic, study staff will have a randomization code within the tablet system used for data collection. Following completion of the baseline assessment, the computer will generate the next randomization group. Randomization will be blocked to ensure that roughly equal numbers end up in each arm. The computer will also generate the randomization assignment for the Randomization ID assigned to the patient (and subsequently linked with their Screening ID). Randomization IDs and assignments will be generated *a priori* by a U.S.-based study team member and linked into the computer system. We will inform the participant of their assignment immediately after the baseline assessment. Those participants who are assigned to CETA will then be asked whether they want to invite a partner and if so, will be given the information sheet and forms to be completed and returned by their partner. Because randomization will occur only after the baseline assessment, some subjects may drop out before randomization, which will be tracked.

k. Study Arms: Common Elements Treatment Approach (CETA)

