Themba Lethu clinic alone has about 4000 female patients, while other clinics have similar numbers of patients. Of these, about 1000 had an unsuppressed viral load in the past year. We anticipate that 50% of those we screen will be eligible for the study and of those 50% will enroll. We therefore estimate we will need to **screen approximately 1600 patients** over 18 months, requiring us to screen about 20 patients and enroll approximately 5 patients per week over the enrollment period.

Given we are randomizing 400 women and including up to 100 men, the total sample size for the IRB will be 500.

The IPV literature strongly suggests that more needs to be done with perpetrators of violence (not just survivors), and we know from studies like ours in Zambia that helping male partners led to many positive changes on outcomes, and from the perspective of the women. However, for this study, we wanted the choice to be the womans' – for ethical and safety reasons. Therefore, we could not confirm the ultimate number of male participants we would have.

Sample Size – Qualitative Study Component

For the FGDs and IDIs we will purposively select participants from the main study. We will recruit a total of 40 participants from the treatment arm who completed the trial in 2023. There will be 3 FGDs, with 6-10 participants in each FGD, and 10 IDIs with study participants. We will also recruit 5 CETA providers and 5 healthcare providers who supported referral to CETA from Themba Lethu Clinic and Zola clinic (adherence counselors), for in-depth interviews.

d. Primary Analysis

All primary analyses will be by intention-to-treat. The unit of analysis will be the woman. Our primary analysis will be a comparison of risk differences with 95% confidence intervals. If we identify differences (RD) in baseline covariates we will conduct an adjusted linear regression to get an adjusted RD.

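### The step from 150 willing women to 75 partnered CETA women makes no allowance for partners who do not enrol, and 75 per group gives about 73% power for 21 points, not 80%

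*Combined protocol and SAP*

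**What the plan says.** The Sample Size section (Data Analysis, c) and the Summary both link the sample size to the partner question: "we have calculated our sample size to ensure our ability to detect differences separately among women who include a partner". The total is raised to 400, with at least 75 and at most 100 CETA women who include a partner, "which will give us 80% power to detect an absolute 21% difference between arms in women with partners". The recruitment need is then given as: "To get 75 women who include partners in the CETA arm we will have to randomize about 150 women willing to include a partner". The control rate is set by this statement: "we estimate that only 40% of those who are unsuppressed will be retained in care and virally suppressed 12 months post-baseline". The test is a two-sided 5% chi-squared test, and the Full Consent section gives 50-50 allocation.

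The same section later explains that the choice to involve a man was left to the woman for ethical and safety reasons, and adds: "Therefore, we could not confirm the ultimate number of male participants we would have".

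The procedures describe how a partner comes in. Willingness is asked at consent, before randomization (Male Partners). After assignment there is a second decision: "Those participants who are assigned to CETA will then be asked whether they want to invite a partner". The woman takes an information sheet home. "Those men who are willing to know more about the study and potentially participate will be asked to either attend information sessions", or else phone the study or return a form. He must then meet the male eligibility criteria (own unshared phone, literacy in a study language, psychiatric and suicidality exclusions) and consent. The Moderator Analysis section compares CETA women who actually included a partner with control women who said they would have done so.

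**The concern.** Halving 150 gives 75, so the only factor applied is the allocation ratio. Women who are willing and women who include a partner are treated as the same number, although the protocol asks the woman again and then depends on a second person to respond, qualify and consent. Each willing CETA woman whose partner does not enrol leaves the analysed CETA group, because that group is defined by actual inclusion.

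Partner involvement is the primary moderator (Aim 2), and both the Summary and the Sample Size section use it to justify the size of the trial. If a non-significant subgroup result is read against a claim of 80% power, it may be given more weight as evidence of no effect than the numbers allow.

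**Working it through.** **Inputs.** From Sample Size: control rate 40%; difference 21 points, so 61% under CETA; two-sided 5%; 75 partnered CETA women; about 150 willing women. Allocation 1:1 (Full Consent). The proportion u of willing CETA women whose partner enrols is not in the documents. I assume 50% to 100%.

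**The head count.** Expected partnered CETA women = 150 × 0.5 × u = 75u, which equals 75 only at u = 100%. For an expected 75, the willing number must be 150/u.

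The Randomization section describes blocking but no stratification by willingness. If exactly 150 of 400 women are willing and 200 go to each arm, the chance of at least 75 partnered CETA women is about 54% at full conversion, 8% at 90% and 0.3% at 80%.

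**The stated power, at full conversion.** Power = Φ[(d − 1.96 × SE0)/SE1], with SE0 pooled and SE1 unpooled.

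- Pooled rate = (0.40 + 0.61)/2 = 0.505
- SE0 = √(2 × 0.505 × 0.495/75) = 0.0816
- SE1 = √((0.40 × 0.60 + 0.61 × 0.39)/75) = 0.0798
- (0.21 − 1.96 × 0.0816)/0.0798 = 0.63, so power is 73.4%

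The unpooled version gives 74.9% and exact enumeration of the chi-squared test gives 74.8%, so the choice of formula does not explain the gap. The same formula solved for 80% power gives 88 per group, or a detectable difference of 22.7 points at 75 per group.

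Other inputs come near 80%: 75 CETA against 100 controls gives 79.1%, and 75 per group at 20% against 41% gives 80.4%. Neither is the stated 40% control rate with 150 willing women split 1:1.

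**Adding conversion.** Scenario A fixes 150 willing women, so there are 75u partnered CETA women against 75 willing controls. Scenario B recruits 150/u willing women, so there are 75 partnered CETA women against 75/u willing controls. Both use 40% against 61%.

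| u (assumed) | A: partnered CETA | A: power | A: detectable difference (points) | B: willing women needed (share of 400) | B: power |
|---|---|---|---|---|---|
| 100% | 75 | 73% | 22.7 | 150 (37.5%) | 73% |
| 90% | 67.5 | 71% | 23.3 | 167 (42%) | 76% |
| 80% | 60 | 68% | 24.0 | 188 (47%) | 78% |
| 70% | 52.5 | 65% | 24.9 | 215 (54%) | 80% |
| 60% | 45 | 61% | 26.1 | 250 (62.5%) | 83% |
| 50% | 37.5 | 56% | 27.6 | 300 (75%) | 85% |

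In A, incomplete conversion costs about 5 points of power at 80% (73.4 − 68.3) and about 18 at 50% (73.4 − 55.8). In B, power rises as u falls because the willing control group grows.

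**The case against.** The strongest reply is that 150 is a planning estimate. Nothing stops recruitment of willing women at 150, and any of the 400 may be willing. If the minimum of 75 is met, power is between 73% and 85%, and it reaches 80% at u of about 70% or below. The plan's upper limit of 100 partnered women also leaves room for the 88 per group that 80% power needs. This stands. It means that the minimum is unsupported by the stated step, not that it fails. The recovery in power concerns precision only, since actual includers would still be set against merely willing controls, a comparison that randomization does not protect.

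The plan also discloses that the number of men is uncertain and explains why, and it reports that in the team's Zambian work many men enrolled and stayed. Disclosure of HIV status to the partner is the woman's own entry criterion, so it is arguably settled before any later loss. These points are fair, but they supply no conversion rate, and the minimum and the power are still stated without condition.

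Three stronger readings are tempting, and the documents support none of them.

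- A reader might infer that uptake was well below what 75 requires. No rate is given, and the 50% to 100% range is mine.
- A reader might attribute the whole gap to 80% to conversion. The drop from 80% to 73% is there at full conversion.
- A reader might dilute the 21 points across all willing women as randomized. The Moderator Analysis does not specify that comparison, and the dilution would assume that CETA does nothing without a partner, contrary to the Aim 1 hypothesis.

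Finally, risk differences within moderator levels are already planned, and the primary comparison in all 400 women is unaffected: 200 per arm gives about 98% power for 40% against 60%.

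**Conclusion.** The point holds in two limited parts. First, the step from 150 to 75 builds in full conversion, and the protocol's own recruitment steps make some loss likely, so 150 does not support an unconditional minimum of 75. Whether 75 was reached cannot be judged from the documents.

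Second, and independently of conversion, 80% power for 21 points does not follow from the stated inputs at 75 per group: it is about 73%. If the trial had only 150 willing women, power would fall to 68% at 80% conversion and 56% at 50%. If it reached 75 partnered women by recruiting more willing women, power would be 78% and 85% at the same rates.

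These figures rest on the 40% control rate, a 21-point effect, the two-sided 5% test, and an assumed conversion range. The error affects the subgroup claim used to justify the size of the trial, not the primary analysis.

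**What to change.** In Sample Size, define u as the proportion of willing CETA women whose partner enrols, state the value assumed, and give the willing number as 150/u over a range (for example 188 at 80%, 250 at 60%, 300 at 50%). Replace the unconditional 80% with power and detectable difference at the numbers of partnered CETA women and willing controls actually enrolled, noting about 73% and 22.7 points at 75 against 75. The monitoring section reports one-year follow-up complete by March 2025, so these counts should be obtainable.

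Align the Summary, which puts 80% power for 21 points beside the total of 400 without saying that it refers to women with partners. State that the partner-subgroup result will be reported as a risk difference with its 95% confidence interval, and that non-significance will not be read as no partner effect.

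The cost is wording in two places and a less favourable power figure at 75 per group. No further participants or data are needed. The change cannot alter recruitment, and its use now is in how the subgroup result is read.
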